6.7.3. Management of Hyperammonemia

Participants receiving INCB001158 as monotherapy or in combination with daratumumab SC should be monitored for elevated venous plasma ammonia. Asymptomatic clinically significant drug-related elevations in ammonia (eg, a repeatable elevation in ammonia $> 2 \times$ ULN AND $> 2 \times$ baseline) should be managed by interrupting INCB001158 and monitoring to resolution. For symptomatic elevations (ie, significant ammonia elevation associated with nausea, vomiting, severe anorexia, mental status changes, seizure, or other symptoms associated with hyperammonemia), participants should be admitted for management according to the local institutional protocol for hyperammonemia, including 1) sending appropriate laboratory samples (ammonia [on ice, measured immediately], plasma amino acid profile, liver function tests, electrolytes, bicarbonate, BUN or urea, creatinine, glucose, and urine orotic acid), 2) IV hydration with dextrose-containing fluids, 3) discontinuation of protein intake, 4) implementing therapy to reduce ammonia levels (oral lactulose/lactitol, IV Ammonul[®]), and 5) identifying and treating any potential triggers (eg, discontinue corticosteroids, treat infections).

6.7.4. Dose Delays and Dose Modification of Daratumumab SC

Dose modification of daratumumab SC is not permitted. Dose delay is the primary method for managing toxicities related to daratumumab SC.

On the first day of each new treatment cycle and before each daratumumab SC administration, the participant will be evaluated by the treating physician for possible toxicities that may have occurred after the previous dose(s). Toxicities are to be assessed according to CTCAE v5. Dose delays will be made based on the toxicity experienced during the previous cycle of therapy or newly encountered on Day 1 of a cycle.

For all daratumumab SC doses in a treatment cycle except the first dose, if daratumumab SC administration does not commence within the prespecified window (see [Table 3](#) and [Table 4](#) for study site visit assessments prior to and post-crossover, respectively, and [Table 7](#) for all participants as of Protocol Amendment 3) of the scheduled administration date, then the dose will be considered a missed dose. Administration may resume at the next planned dosing date. A missed dose will not be made up. The minimal time interval between daratumumab SC doses should be 4 days.

Daratumumab SC treatment must be held if any of the following criteria below are met, to allow for recovery from toxicity, regardless of relationship to INCB001158 or daratumumab SC.

- Grade 4 hematologic toxicity, except for Grade 4 lymphopenia
- Grade 3 thrombocytopenia with bleeding
- Febrile neutropenia
- Neutropenia with infection, of any grade
- Grade 3 or higher nonhematologic toxicities, *with the following exceptions:*
 - Grade 3 nausea or Grade 3 vomiting that responds to antiemetic treatment within 7 days
 - Grade 3 diarrhea that responds to antidiarrheal treatment within 7 days

- Grade 3 fatigue that was present at baseline or that lasts for < 7 days after the last administration of daratumumab SC
- Grade 3 asthenia that was present at baseline or that lasts for < 7 days after the last administration of daratumumab SC.

Administration of daratumumab SC may be restarted (as indicated in [Table 18](#)) upon recovery from toxicity to Grade 2 or baseline, with the exception that Grade 2 laryngeal edema or Grade 2 bronchospasm must be fully recovered.

Table 18: Daratumumab SC-Related Toxicity Management

Cycles	Frequency	Dose Held	Dosing Re-Start at
1 and 2	QW	> 3 days	Next planned QW dosing date
3 to 6	Q2W	> 7 days	Next planned Q2W dosing date
7+	Q4W	> 14 days	Next planned Q4W dosing date

The cycles may be delayed up to 4 weeks (Cycle 1 to Cycle 6) or up to 6 weeks (Cycle 7 and beyond). If Day 1 of a cycle is delayed, Day 1 of subsequent cycles should be adjusted accordingly to maintain the 28-day cycle duration. However, if a within-cycle dose is delayed, then the dates of the subsequent within-cycle doses should not be adjusted. [REDACTED]

[REDACTED]

[REDACTED]

When daratumumab SC is held, INCB001158 may be continued, at the investigator's discretion with approval of the medical monitor.

6.7.5. Daratumumab SC Interruption or Missed Doses

A daratumumab SC dose that is held for more than the permitted time (see [Table 18](#)) from the per-Protocol administration date for any reason other than toxicities suspected to be related to daratumumab SC should be brought to the attention of the sponsor at the earliest possible time. Participants whose dose was delayed for more than 4 weeks (Cycle 1 to Cycle 9) or 2 consecutive planned doses (after Cycle 9) should have daratumumab SC discontinued, unless, upon consultation with the sponsor and the review of safety and efficacy, continuation is agreed upon.

6.8. Concomitant Medications and Procedures

All concomitant medications and treatments (including over-the-counter or prescription medicines, vitamins, vaccines, and/or herbal supplements) must be recorded in the eCRF. Any prior medication received up to 30 days before the first dose of study treatment and 30 days after the last dose of the last study treatment, or until the participant begins a new anticancer therapy, whichever occurs first, will be recorded in the eCRF. Any addition, deletion, or change in the dose of these medications will also be recorded. Concomitant medications administered after 30 days after the last dose of study treatment should be recorded for SAEs as defined in [Section 9.4](#). Concomitant treatments/procedures that are required to manage a participant's medical condition during the study will also be recorded in the eCRF. The medical monitor should be contacted if there are any questions regarding concomitant or prior therapy.

NOTE: As of Protocol Amendment 3, use of concomitant medications should be monitored for participants to verify that they are not taking any concomitant medication prohibited per Protocol; however, concomitant medications no longer need to be collected in the eCRF, except for concomitant medications in relation with SAEs or AESIs.

6.8.1. Permitted Medications and Procedures

All treatments that the investigator considers necessary for a participant's welfare may be administered at the discretion of the investigator in keeping with the community standards of medical care. All concomitant medication will be recorded on the eCRF including all prescription, over-the-counter, herbal supplements, and IV medications and fluids. If changes occur during the study period, documentation of drug dosage frequency, route, and date will also be included on the eCRF.

6.8.1.1. Bisphosphonate Therapy

Bisphosphonate therapy is strongly recommended for all participants with evidence of lytic destruction of bone or with osteopenia. Bisphosphonate therapy is recommended to be continued according to treatment guidelines ([NCCN 2014](#)). Commercially available IV bisphosphonates (pamidronate and zoledronic acid) are preferred when available and should be used according to the manufacturer's recommendations, as described in the prescribing information, for participants with osteolytic or osteopenic myelomatous bone disease. Oral bisphosphonates may be used as alternatives if IV bisphosphonates are not available at the study site. It is preferred that investigators use the same route of bisphosphonate therapy for all participants at their sites. Participants who are using bisphosphonate therapy when they enter the study should continue the same treatment. Participants with evidence of lytic destruction of bone or with osteopenia who are not using a bisphosphonate at the time of administration of study treatment should start a bisphosphonate as soon as possible during Cycle 1 or 2 of treatment. Investigators should not start bisphosphonate therapy during the study, unless it has been agreed with the sponsor that there is no sign of disease progression.

6.8.1.2. Therapy for Tumor Lysis Syndrome

Participants should be monitored for symptoms of tumor lysis syndrome. Management of tumor lysis syndrome, including dehydration and abnormal laboratory test results such as hyperkalemia, hyperuricemia, and hypocalcemia, are highly recommended. It is also recommended that high-risk participants (ie, those with a high tumor burden) should be treated prophylactically in accordance with local standards (eg, rehydration, diuretics). Xanthine oxidase inhibitors (eg, allopurinol) are not allowed (see Section [6.8.2](#)), as they cause an accumulation of orotic acid in the urine, which would confound assessment of safety in these participants. Participants will receive prophylactic therapy to prevent IRRs during the treatment period, as described in Section [6.5.1](#).

6.8.1.3. Management of Hepatitis B Virus Reactivation

For participants who are diagnosed with HBV reactivation while on treatment, daratumumab SC should be interrupted until the infection is adequately controlled. If the benefits outweigh the risks, daratumumab SC may be resumed with concomitant antiviral prophylaxis as per local standard of care and in consultation with the medical monitor.

6.8.2. Prohibited Medications and Procedures

Medications or vaccinations specifically prohibited in the exclusion criteria are not allowed during the ongoing study. If there is a clinical indication for any medication or vaccination specifically prohibited during the study, discontinuation from study therapy may be required. The investigator should discuss any questions regarding this with the medical monitor. The final decision on any supportive therapy or vaccination rests with the investigator and/or the participant's primary physician. However, the decision to continue the participant on study treatment requires the mutual agreement of the investigator, the medical monitor, and the participant.

Participants are prohibited from receiving the following therapies during the screening and treatment of this study:

- Investigational treatments or commercially available agents with activity against or under investigation for MM.
- Live vaccines within 30 days before the first dose of study treatment, while participating in the study, and until 3 months after the last dose of study treatment.
 - Examples of live vaccines include, but are not limited to, the following: measles, mumps, rubella, chickenpox, yellow fever, nasal seasonal flu, nasal H1N1 flu, rabies, *Bacillus Calmette-Guérin*, and typhoid.
- Except for erythropoietin or darbepoetin alpha (Aranesp[®]), use of growth factors (G-CSF, GM-CSF, etc) is not permitted in the first treatment cycle unless the participant experiences a hematologic DLT.
- Typically, IV contrast is not used in CT scanning of participants with secretory MM because of the risk to the kidney. If administration of IV contrast is necessary, then adequate precautions including hydration are indicated.
- Concomitant treatment with valproic acid/valproate-containing therapies is not permitted, as hyperammonemia is a well-described toxicity of valproic acid, particularly at high exposures, potentially through inhibition of the urea cycle ([Verrotti et al 2002](#), [Wadzinski et al 2007](#)).
- Concomitant treatment with allopurinol or other xanthine oxidase inhibitors is not allowed. Xanthine oxidase inhibitors (eg, allopurinol) cause an accumulation of orotic acid in the urine, which would confound the assessment of safety in these participants.
- Prolonged therapy with systemic glucocorticoids (> 7 days) for any purpose other than to modulate symptoms from an AE, SAE, or event of clinical interest, or for use as pre- and post-administration medications. Brief, limited use of systemic corticosteroids (≤ 7 days) are permitted where such use is considered standard of care.
 - Replacement doses of steroids (for example, prednisone 5 to 7.5 mg daily) are permitted while on study, as is the use of local steroids.

Participants who, in the assessment by the investigator, require the use of any of the aforementioned treatments for clinical management should be removed from treatment but should continue in the study for assessment of disease status and survival.

There are no prohibited therapies during the post-treatment follow-up period.

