Urine sample for orotic acid	X	X*	X*		X				See Table 23 for sample collection times. * Cycle 1 only. Additional samples may be collected as clinically indicated. See Section 8.3.7.3 .			

Table 7: Schedule of Activities for All Participants (as of Protocol Amendment 3)

Procedure	Protocol Section	Treatment	EOT	Safety Follow-Up	Notes
		(28-Day Cycle)	+ 7 d	28-35 d After EOT	
Informed consent	8.1.1	X			Participants will sign a new ICF as per Protocol Amendment 3.
Contact IRT	8.1.3	X	X		
Concomitant medications	6.8	X	X	X	Review to ensure no prohibited medications are being used. Provide data to sponsor about medications used for SAEs and AESIs only.
Distribute reminder cards	8.1.4	X*	X		*On the clinic days for the next visit.
Assess study treatment compliance	6.4	X*	X		*Day 1 of each cycle.
Dispense/administer INCB001158 (participants receiving INCB001158 monotherapy or in combination with daratumumab SC)	6.1	X			On clinic day, INCB001158 should be given just before administration of daratumumab SC (if applicable). See Appendix B and Pharmacy Manual.
Administer daratumumab SC at site (participants receiving daratumumab SC monotherapy or in combination with INCB001158)	6.1	X			In clinic, daratumumab SC should be administered after INCB001158. See Appendix C and Pharmacy Manual.
AE assessments	8.3.1	X	X	X	All SAEs and AESIs must be recorded in the eCRFs, regardless of the causal relationship.
Efficacy/disease assessments (blood/urine/other)	8.2.1	X	X		As of Protocol Amendment 3, the disease assessments are only required to be performed as per standard of care guidelines for the participant's condition and monitoring.
Pregnancy testing	8.3.7.5	X*	X		All female participants of childbearing potential. *Urine at Day 1 of each cycle, at EOT, and as medically indicated or per country or institutional requirements.
Post-treatment anticancer therapy status	8.8.2			X	If a participant is scheduled to begin a post-treatment anticancer therapy before the end of the safety follow-up period, then the safety follow-up visit should be performed before post-treatment anticancer therapy is started.

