8.8. Follow-Up

8.8.1. Safety Follow-Up

The safety follow-up period is the interval between the EOT visit and the scheduled follow-up visit, which should occur 28 to 35 days after the EOT visit (or after the last dose of study treatment if the EOT visit was not performed). Adverse events and SAEs must be reported up

until 1) at least 28 days after the last dose of study treatment and 90 days for irAEs or the start of a new anticancer therapy or 2) until toxicities resolve, return to baseline, or are deemed irreversible, whichever is longer. Reasonable efforts should be made to have the participant return for the follow-up visit and report any AEs that may occur during this period. If the participant cannot return to the site for the safety follow-up visit, the participant should be contacted by telephone for assessment of AEs and SAEs, and this contact should be documented in the source.

If a participant is scheduled to begin a new anticancer therapy before the end of the 28- to 35-day safety follow-up period, the safety follow-up visit should be performed before a new anticancer therapy is started. Once a new anticancer therapy has been initiated, the participant will move into the survival follow-up period.

NOTE: As of Protocol Amendment 3, data will only be collected for SAEs, AESIs, and pregnancy. Once a new anticancer therapy has been initiated, the participant will no longer be followed for survival follow-up beyond the last safety follow-up visit.

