8.8.2. Disease Status Follow-Up

Participants who discontinue study treatment for a reason other than disease progression will move into the disease status follow-up period and should be assessed every 8 weeks \pm 7 days after EOT to monitor disease status. Every effort should be made to collect information regarding disease status until:

- The start of new anticancer therapy.
- Disease progression.
- Death.
- The end of the study.

NOTE: As of Protocol Amendment 3, disease status follow-up visits for participants who discontinue study treatment for a reason other than disease progression are no longer required beyond the safety follow-up visit. The last disease status follow-up data will be recorded in the eCRF at the time of the safety follow-up visit. The last study visit will be the safety follow-up visit.

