11. SUPPORTING DOCUMENTATION AND OPERATIONAL CONSIDERATIONS

11.1. Investigator Responsibilities

- The Protocol, Protocol amendments, ICF, IB, and other relevant documents (eg, advertisements) must be submitted to an IRB/IEC by the investigator and reviewed and approved by the IRB/IEC before the study is initiated.
- The investigator is responsible for ensuring that the safety reports provided by the sponsor are reviewed and processed in accordance with regulatory requirements, the policies and procedures established by the IRB/IEC, and institutional requirements.
- Any amendments to the Protocol will require IRB/IEC approval before implementation of changes made to the study design, except for changes necessary to eliminate an immediate hazard to study participants.
- The investigator will be responsible for the following:
 - Providing written summaries of the status of the study to the IRB/IEC annually or more frequently in accordance with the requirements, policies, and procedures established by the IRB/IEC.
 - Notifying the IRB/IEC of SAEs or other significant safety findings as required by IRB/IEC procedures.

- Providing oversight of the conduct of the study at the site and adherence to GCP, IRB/IEC requirements, institutional requirements, and applicable laws and country-specific regulations.
- Adhering to the Protocol as described in this document and agreeing that changes to the Protocol procedures, with the exception of medical emergencies, must be discussed and approved, first, by the sponsor or its designee and, second, by the IRB/IEC. Each investigator is responsible for enrolling participants who have met the specified eligibility criteria.
- Retaining records in accordance with all local, national, and regulatory laws, but for a minimum period of at least 2 years after the last marketing application approval in an ICH region and until there are no pending or contemplated marketing applications in an ICH region, or if not approved, 2 years after the termination of the test article for investigation to ensure the availability of study documentation should it become necessary for the sponsor or a regulatory authority to review.

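### Section 6.8.2 bans live vaccines until 3 months after the last dose, yet its list header and closing sentence confine or remove prohibitions once treatment ends

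*Protocol*

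**What the plan says.** Three statements in Protocol Section 6.8.2 bear on the point, all in current text.

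- The list header: "Participants are prohibited from receiving the following therapies during the screening and treatment of this study".
- The live-vaccine bullet under that header. It starts 30 days before the first dose and then runs "while participating in the study, and until 3 months after the last dose of study treatment".
- The last sentence of the section: "There are no prohibited therapies during the post-treatment follow-up period".

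Section 8.8.1 defines one follow-up period: "The safety follow-up period is the interval between the EOT visit and the scheduled follow-up visit, which should occur 28 to 35 days" after EOT, or after the last dose if no EOT visit took place. Sections 8.8.2 and 8.8.3 describe disease status and survival follow-up. Amendment 3 ends the requirement for both beyond the safety visit, and its note in Section 8.8.2 adds: "The last study visit will be the safety follow-up visit". Table 7, the only schedule in force since Amendment 3, marks concomitant medications at safety follow-up, with the note "Review to ensure no prohibited medications are being used".

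**The concern.** A site deciding about a live vaccine shortly after a participant stops treatment finds two answers in one section. The bullet says no. The closing sentence says that nothing is prohibited at that stage, and the header agrees with it by stopping the list at the end of treatment.

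The section can itself bring a participant to this point. It directs that anyone who needs a listed treatment be taken off study treatment but kept in the study, which is where the bullet and the closing sentence part.

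What is at stake is a restriction that the sponsor chose to extend past the last dose. Sites should not have to guess whether it still applies.

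**Working it through.** The plan gives no figure to reproduce. The check sets the statements side by side and compares their time windows.

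**Inputs**

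- Ban: throughout participation, and until 3 months after the last dose (Section 6.8.2). I take 3 months as 91 days; counting conventions give 84 to 92.
- Safety follow-up: from EOT to a visit 28 to 35 days later (Section 8.8.1).
- Disease status follow-up: every 8 weeks ± 7 days after EOT, no longer required beyond the safety visit under Amendment 3 (Section 8.8.2). Survival follow-up is cut back at the same point (Section 8.8.3).

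**Step 1: do the statements cover the same things?** Yes. The header calls the listed items therapies, and live vaccines are on the list. The closing sentence uses the same word, so reading vaccines as something other than therapies does not separate the two.

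**Step 2: do the periods overlap?** The protocol does not define the phrase used in the closing sentence. There are three readings:

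| Meaning of the follow-up phrase | Overlap with the ban |
|---|---|
| All time after the last dose | day 0 to day 91, about 91 days |
| Safety follow-up only | 28 to 35 days, fewer if the visit is brought forward for new anticancer therapy |
| Disease status and survival follow-up only | possibly little or none for ongoing participants under Amendment 3 |

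On the second reading, the 3-month limb alone covers the whole interval if EOT is no later than 91 − 35 = 56 days after the last dose. If EOT is later, the participation limb still covers it, because the safety visit is the last study visit.

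On the third reading, the overlap was real before Amendment 3. The first disease status visit fell at 56 ± 7 = 49 to 63 days after EOT, inside the 91 days whenever EOT was within 91 − 63 = 28 days of the last dose. With those visits no longer required beyond the safety visit, that overlap largely goes.

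**Step 3: what must an exception contain?** Suppose it carried only the 3-month limb. From Cycle 7, daratumumab is given every 28 days and a cycle may be delayed by up to 6 weeks (Section 6.7.4), so EOT could fall about 28 + 42 = 70 days after the last daratumumab dose. The safety visit would then be at 70 + 28 = 98 to 70 + 35 = 105 days, which is 7 to 14 days past day 91. On those days the bullet would still ban a live vaccine through its participation limb and the closing sentence would not. The example assumes that daratumumab is the participant's only remaining study treatment; continued INCB001158 would move the last dose later. The exception therefore needs both limbs.

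**The case against.** The strongest reply is that the specific rule governs the general one. The live-vaccine bullet is the only item on the list with its own end date after the last dose, and that date would be pointless if the closing sentence cancelled it. The Table 7 check at safety follow-up also has little left to check unless some prohibition still runs, so it reminds sites that restrictions can outlast treatment. Section 6.8.2 sends questions to the medical monitor. This is a sensible way to read the text, and many sites would read it so. It does not remove the defect, because the protocol never says that the bullet prevails and the header points the other way.

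A second reply is that the closing sentence follows one about disease status and survival assessment, so it may refer only to those periods. That stands as a possible reading. A reader might infer that the conflict must last at least 28 to 35 days, but this holds only if the phrase includes safety follow-up, which the documents do not settle.

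A third reply is that the practical value is small. That also stands. The rationale for Amendment 3 says enrollment has ended, and the SAP of 19 APR 2022 plans safety analyses and efficacy listings only. Nothing in the documents shows that another amendment is coming.

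**Conclusion.** The contradiction is real and minor. The overlap ranges from about 91 days down to possibly none for ongoing participants, depending on the meaning of an undefined phrase and on taking 3 months as 91 days. These counts measure how long the statements disagree, not harm; the documents do not say how many ongoing participants might need a live vaccine.

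A reader might infer that the protocol permits live vaccines once treatment stops. It does not do so cleanly, since the bullet forbids them in equally plain words; the fault is that both statements stand. Nor is there support for any effect on the trial's results: no endpoint, error rate or analysis depends on this rule.

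**What to change.** Keep the ban and make two wording changes in Section 6.8.2.

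1. Open the closing sentence with: *Except for live vaccines, which remain prohibited throughout study participation and for 3 months after the final dose of study treatment,* and let the rest of the sentence follow unchanged.
2. Add to the list header, after its reference to screening and treatment: *(and beyond, where stated)*.

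The first change removes the conflict on all three readings because it carries both limbs of the bullet. The second stops the header from cutting off a ban that the bullet extends.

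The cost is two short edits, with no added visit, data collection or analysis. Section 11.1 sets the procedure: "Any amendments to the Protocol will require IRB/IEC approval before implementation of changes made to the study design". The edits belong in the next amendment, if there is one; opening an amendment for them alone would be out of proportion. Until then, the medical monitor, to whom Section 6.8.2 already directs such questions, can give sites the same answer.
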